5.3.4 Analysis

Using Sawtooth software 'SSI software platform' the partial utilities ("partworths") for elements of RMC will be determined – the 'SSI software platform' includes analysis instrument for choice-based conjoint-analysis. Partworths utilities derived will be used to compute the total utilities associated

⁷Orme B. Sample size issues for conjoint analysis studies. Sequim: Sawtooth Software Technical Paper; 1998.

with each dimension of respectful care and their relative importance as attributes of RMC. Table 8 highlights the analysis planned.

Table 7. Analysis plan

Research questions	Data sources	Analysis
Objective 3 – What is the utility associated with global dimensions of respectful maternity care in facility-based childbirth in Gombe?	Choice experiment (from household follow up)	 Descriptive statistics to characterize the study sample in numbers & percentages Generate individual level estimates of the part-worth of each mother's utility function from household follow up Determine the value associated with each dimension of RMC from household follow up Segmentation/sub-group analysis based on mother's sociodemographic characteristics For the choice-based conjoint analysis, maximum likelihood estimation and logistic regression will be conducted.

6 Field procedures & data management

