this design heterogeneity could be confounded in case of taste heterogeneity and scale differences.¹ Table 3 describe the steps involved.

Table 6. Steps and activities involved

Steps	Activities
Identifying attributes	Identify dimensions or attributes of RMC through qualitative research involving (1) review of published and grey literature and (2) focus group discussion with the target population to augment the secondary data. Example of attributes of RMC includes physical abuse, non-consented care, non-confidential care, non-dignified care.
Assigning attribute levels	Use information generated from qualitative methods above to assign attribute levels. Attribute levels will reflect the range of RMC situations that mothers are likely to experience, e.g. attribute levels for non-dignified care: harsh tone; harsh language; unkind expression. To aid cognition each attribute will have not more than three levels.
Generating the choice sets	Use conjoint Sawthooth software to generate attribute level combination to create hypothetical scenarios — create choice sets. To obtain orthogonal and balance design fractional factorial design will be used.
Pre-testing the questionnaire and data collection	Pre-test, evaluate the process and revise the survey. Use trained fieldworkers to administer the questionnaire to respondents.
Analysing of DCE data	Generate individual level estimates of the part-worth of each mother's utility function. Determine the value associated with each dimension of RMC. Perform segmentation/sub-group analysis based on mother's sociodemographic characteristics.

Sample – the choice experiment will be administered during home follow-up interviews: during follow-up at home in November December 2017 to the same post-partum women with live birth that were observed during childbirth and interview at exit in July 2017.

Sample size – For the choice-based experiment, suggestion of sample size determination by Johnson and Orme will be used, which suggests that the sample size required for the main effects depends on the number of choice tasks (t), the number of alternatives (a), and the largest number of levels for any of the attributes (c) according to the following equation: N>500c/(t×a),⁷ if t =15 (i.e. 15 choice tasks) and a =2 (i.e. # of alternatives) and c =6 (i.e. largest # of levels), then the required sample size =500x6 \div 15x2 =100.

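### Choice experiment: part-worths are promised for each mother, but the only estimator named ordinarily gives aggregate part-worths and makes no provision for one woman's repeated choices

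*Protocol*

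**What the plan says.** The woman-level output is promised twice. The last step in Table 6 (Protocol 5.3.3) is to "Generate individual level estimates of the part-worth of each mother's utility function". Table 7 (5.3.4) repeats this for the home follow-up data: "Generate individual level estimates of the part-worth of each mother's utility function from household follow up". Both tables then list the value of each dimension and analyses by sociodemographic subgroup.

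The estimator appears once, as the last entry of Table 7: "For the choice-based conjoint analysis, maximum likelihood estimation and logistic regression will be conducted". The text above that table assigns the part-worths to the Sawtooth platform and says that "the 'SSI software platform' includes analysis instrument for choice-based conjoint-analysis", without saying which estimation method will be used. No mixed logit, hierarchical Bayes or latent-class model is named.

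The data per woman come from 5.3.3. Scenarios are shown in pairs and she picks one of each pair. The sample-size example takes 15 tasks conditionally ("if t =15 (i.e. 15 choice tasks") with two alternatives. Table 6 says that "each attribute will have not more than three levels". The number of attributes is not fixed: Table 6 gives four examples, and the typology in section 1.3 has seven domains.

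**The concern.** The named method and the named output do not match. A logistic regression on everyone's choices estimates one common vector of part-worths. It does not return a vector for each mother. The other literal reading, a separate maximum likelihood fit per mother, asks about 15 binary answers to support all the parameters of the design.

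At stake is the woman-level part of Objective 3. An analyst following Table 7 as worded would either not produce it or find that most women have no estimate. Section 5.2.3 also plans to compare utilities at exit and at six months in the same women; any within-woman version of that comparison would meet the same difficulty.

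A second, smaller matter is that Table 7 makes no provision for repeated answers from one woman, although 5.3.3 itself mentions possible taste heterogeneity.

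**Working it through.** **The plan's own figure.** The sample-size rule in 5.3.3 is N > 500c/(t × a). With c = 6, t = 15, a = 2: 500 × 6 / (15 × 2) = 3000/30 = 100, as stated. The rule is described as applying to main effects; it says nothing about estimating each woman's utilities. (With Table 6's cap of three levels the same rule gives 500 × 3/30 = 50. The conflict between six and three levels should be reconciled but does not drive this point.)

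**Information per woman.** Fifteen tasks with two alternatives give 15 binary answers. A main-effects model with A attributes of L levels needs A × (L − 1) parameters:

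- four 3-level attributes: 4 × 2 = 8
- five: 5 × 2 = 10
- seven: 7 × 2 = 14

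**Does a woman-level maximum likelihood estimate exist?** Let z_t be the attribute vector of the chosen scenario minus that of the rejected one in task t. A finite, unique estimate exists only if the design has full rank and no vector b gives z_t′b ≥ 0 in all 15 tasks with strict inequality in at least one (no separation). This was checked by linear programming on simulated women. Assumptions: randomly paired scenarios, effects coding, true part-worths drawn from N(0, SD) with SD 0.5 or 1.0, 400 women per setting.

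| Design | Parameters | No finite estimate (SD 0.5 to 1.0) |
|---|---|---|
| two 2-level | 2 | 24% to 49% |
| two 3-level | 4 | 49% to 81% |
| three 3-level | 6 | 78% to 91% |
| four 3-level | 8 | 92% to 98% |
| five 3-level | 10 | 99% to 100% |
| seven 3-level | 14 | 100% |
| one 6-level | 5 | 89% to 93% |

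The small designs are sensitive to how pairs are built. Excluding pairs of identical scenarios lowers the first row to about 10% at SD 0.5, and an independent repeat put three 3-level attributes at 71% to 92%. Hence the rounded ranges of 10% to 50% and 70% to 90%. Scaling matters too: with dummy coding, the same SD implies smaller utility gaps, and a check gave about 50% to 82% with three 3-level attributes, 81% to 95% with four and still 97% to 99% with five.

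**Pooled fit, repeated answers ignored.** The target of 320 women gives at most 320 × 15 = 4,800 choices before loss to follow-up; the stated minimum of 100 gives 1,500. Assumptions: five 3-level attributes, mean part-worth 0.3, 300 runs per setting. The model-based standard error is compared with the actual spread of the estimates.

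| Women | Between-woman SD | Model-based SE | Actual SD | Shortfall | Clustered SE |
|---|---|---|---|---|---|
| 100 | 0 | 0.0611 | 0.0621 | 2% | 0.0606 |
| 100 | 0.5 | 0.0564 | 0.0672 | 16% | 0.0644 |
| 100 | 1.0 | 0.0538 | 0.0664 | 19% | 0.0661 |
| 320 | 0 | 0.0340 | 0.0331 | none | 0.0340 |
| 320 | 0.5 | 0.0313 | 0.0359 | 13% | 0.0361 |
| 320 | 1.0 | 0.0299 | 0.0378 | 21% | 0.0370 |

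Shortfall is 1 − model-based/actual, for example 1 − 0.0299/0.0378 = 21%. An independent repeat gave 10% to 18%, so about 10% to 20% overall. With taste variation, nominal 95% intervals covered the pooled model's own target in about 88% to 91% of cases; without it, in 95% to 96%. Clustering by woman brings the standard error close to the actual spread.

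**The case against.** Five points can be made for the plan.

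1. Table 7 lists the individual part-worths and the estimator as separate entries and does not say that the one produces the other. The Sawtooth method is left open, and a mixed logit is itself fitted by (simulated) maximum likelihood. This stands to the extent that the wording does not rule out a suitable model. It does not name one either, and logistic regression is not how such a model is normally described.

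2. Neither the number of attributes nor the 15 tasks is fixed. This stands, and is why the result is given as a range. A very small design would let many women be fitted, though imprecisely. The four example attributes or the seven typology domains would not.

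3. A reader might infer that the plan treats one woman's answers as independent. The protocol never says so. It is silent on variance estimation, a clustered logit would fit its wording, and such detail may sit in an analysis plan that is not shown. Nor would harm follow automatically: without taste variation the unclustered standard errors were right.

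4. A reader might also infer that the subgroup analyses, or Objective 3 as a whole, cannot be delivered. The documents do not support that. Objective 3 asks for utilities of dimensions of care, and pooled models fitted by subgroup, or with covariate interactions, provide them; 5.3.3 already plans to include covariates for this purpose.

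5. Estimation detail can wait for an analysis plan. That would answer a protocol that was silent on the estimator. Here the protocol names an output and an estimator together, and as ordinarily read they do not fit.

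**Conclusion.** The point holds in a limited form. The woman-level part-worths promised in Tables 6 and 7 are not supported by the estimator named in Table 7, ordinarily read. Pooled, it gives aggregate utilities; woman by woman, it would fail for most women in any design near the typology, and for nearly all with five or more 3-level attributes. These shares rest on assumed values: 15 paired tasks, main effects only, effects-coded part-worths with SD 0.5 to 1.0, and randomly built pairs. The clustering effect, about 10% to 20% on the standard error, is conditional on tastes varying between women and on clustering being ignored. Aggregate and subgroup utilities are unaffected as estimable quantities. This is an inexpensive improvement to the plan and does not invalidate Objective 3.

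**What to change.** In Table 7, replace the maximum likelihood and logistic regression line with a random-coefficients model for the paired choices, either mixed logit or hierarchical Bayes, with woman as the panel unit. State that individual part-worths are that model's woman-level estimates, and report the population mean and the between-woman spread of each part-worth. If a pooled logit is kept as a check, use standard errors clustered by woman.

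The cost is one changed line, slightly more analysis work, and possibly slightly wider intervals. Data collection does not change.

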6.1 Recruitment, training and data collectors

IDEAS MLE partner in Nigeria will be responsible for the recruitment, training and management of data collectors, with support from IDEAS staff in Nigeria and London. It is required that data collectors have the requisite language skills appropriate for working in Gombe state. Prior to the data collection, data collectors and supervisors will receive 5 days of training in data collection and on the study tools.

6.2 Field procedures & data management

The study is going to be implemented as part of IDEAS surveys in Gombe state. Except for the focus groups discussions, all survey instruments will be implemented using personal digital assistants (tablets), programmed using CSPro. Confidentiality of every respondent will be guaranteed. Unique identifiers will be constructed for use of the questionnaire and no identifiers will be released. All data will be stored on password-protected computers.

6.3 Ethical Considerations

Risks to study participants for involvement in the study are low. But, questions of disrespect and abuse may evoke emotions, similarly, there is the potential for emotional risks associated with discussion of sensitive questions regarding health and survival of mothers and children. Interviewers will be trained to minimize this risk. Participants will not gain any direct benefits by participating in the study. However, information obtained will be used to improve health service delivery in the community as well as at health facilities.

6.4 Costs and compensation

Respondent will be recruited at home or at the health facility therefore, will not incur any out-ofpocket costs, and no monetary compensation will be given.

6.5 Conflict of interest

There are no other gains from taking part in this study other than the normal scholarly gains.

6.6 Ethical clearance

The study is going to be embedded within the ongoing IDEAS surveys in Gombe. Therefore, ethical clearance from the National Ethics Review Board, Nigeria, and Gombe state Ministry of Health will be obtained together with the IDEAS surveys before the commencement of the study. The study protocol will be reviewed further internally within the IDEAS team.

7. Dissemination plan

Data generated from the study will be shared continuously with implementation partners to inform programming. Similarly, the data will be included in the Gombe results framework to share with other partners. We will seek to engage other groups working to promote respectful care, for example, White Ribbon Alliance, USAID, UKAID and Nigerian association of obstetrics and gynaecology. The result will be presented in Nation and international conferences (depending on opportunities), in scientific journal articles and blog posts.

8. References

- 2. Nigeria. National Population Commission, United States. Agency for International Development, MEASURE DHS (Program). *Nigeria demographic and health survey 2013*. Abuja, Nigeria: National Population Commission; 2014.
- 4. Marchant T. Change in maternal and newborn health care Interactions between families and frontline workers their frequency, quality, and equity, and coverage of interventions for mothers and newborns London School of Hygiene & Tropical Medicine; 2016.
- 5. Nigeria. National Population Commission., ORC Macro. *Nigeria demographic and health survey, 2003.* Abuja, Nigeria Calverton, Md.: National Population Commission; ORC Macro; 2004.
